4. LIST OF ABBREVIATIONS

The following abbreviations are used in this study protocol.

Abbreviation or specialist term	Explanation
AE	adverse event
ANC	absolute neutrophil count
CFR	Code of Federal Regulations
COVID-19	Disease caused by infection with SARS-CoV-2
DSMB	Data and Safety Monitoring Board
eCRF	electronic case report form
EDC	electronic data capture
FDA	Food and Drug Administration
FEV1	forced expiratory volume in 1 second
FVC	Forced Vital Capacity
GCP	Good Clinical Practice
ICH	International Conference on Harmonisation of Technical Requirements for Registration of Pharmaceuticals for Human Use
IRB	Institutional Review Board
MERS	Disease caused by infection with MERS-CoV
ODN	ODN M362
OHRP	Office for Human Research Protections
Pam2	Pam2CSK4
PUL-042	drug product consisting of a 4:1 molar ratio of Pam2:ODN; Inhalation Solution
Pulmotect	Pulmotect, Inc.
RNA	ribonucleic acid
SAE	serious adverse event
SAP	statistical analysis plan
SARS	Disease caused by infection with SARS-CoV
SARS-CoV-2	Coronavirus causing COVID-19
SWFI	sterile water for injection
TLR	Toll-like receptor
USP	United States Pharmacopeia
WHO	World Health Organization

5. BACKGROUND

This protocol is being conducted under a COVID-19 specific IND filed with the Division of Pulmonary, Allergy and Critical Care of the FDA and is intended to provide preliminary data on the efficacy and safety of PUL-042 in reducing the infection rate and progression to COVID-19 in adult subjects exposed to SARS-CoV-2. Evaluation of these data will determine the feasibility of advancing to Phase 3 clinical development to pursue an NDA filing and the potential for Emergency Use Authorization.

This section includes a brief summary of the rationale for clinical investigation of PUL-042 and a summary of the nonclinical data available on PUL-042. More detailed information can be found in the Investigator's Brochure.

5.1. Introduction

Respiratory infection can be caused by a variety of pathogenic organisms including bacteria, fungi, and viruses and is one of the leading causes of death worldwide¹. Even in developed countries, respiratory infection continues to be the leading cause of death from infection and a serious complication for patients being treated for other diseases. The threat of respiratory infections is elevated when there is a decreased level of host resistance such as in immunosuppressed individuals and when there is an increased level of pathogen exposure such as in the case of bioterror attacks and biowarfare or epidemics and pandemics such as the current COVID-19 pandemic.

Pulmotect, Inc. (Pulmotect) has developed a novel therapeutic to stimulate innate immunity in the lungs that may provide protection against lower respiratory tract infection. The technology platform is a direct result of basic research conducted by Pulmotect's founders on the mechanisms of microbial resistance in the lung epithelium^{2,3,4,5,6}. PUL-042 is a combination of two synthetic molecules, a lipopeptide (Pam2CSK4 acetate [Pam2]) and a phosphorothioate oligodeoxynucleotide (ODN M362 sodium [ODN]) that act synergistically as agonists of Toll-like receptors (TLR)2/6 and TLR9, respectively. The response is primarily localized and specific to the site of administration. In animal studies, inhalation treatment with PUL-042 results in increased survival rates after respiratory exposure to a broad spectrum of pathogens including Gram-positive and Gram-negative bacteria (including three Class A bioterror agents), the fungus *Aspergillus fumigatus*, and viral pathogens.

The activity of PUL-042 has been evaluated in animal models against a range of viruses as a single agent⁷ and in combination with existing anti-viral drugs, including oseltamivir against influenza H3N2 for successful treatment at more advanced stages of infection⁸.

Figure 1: Pretreatment with PUL-042 has been demonstrated to protect mice against Influenza A and B

Antiviral activity has also been demonstrated against coronavirus strains. In unpublished experiments conducted at the University of Texas Medical Branch at Galveston (UTMB) a single inhaled dose of PUL-042 was shown to protect mice from SARS-CoV, and significantly reduced the amount of virus in the lungs after infection with MERS-CoV virus (Figure 2). The antiviral activity of PUL-042 therefore has the potential for the prevention of infection with the SARS-CoV-2 virus.

Figure 2: Pretreatment with PUL-042 has been demonstrated to protect mice against SARS-CoV and MERS-CoV

5.2. Chemical Name and Structure

The investigational product, PUL-042 Inhalation Solution, is a combination of Pam2 and ODN. Pam2 is a synthetic 6-amino acid lipopeptide as an acetate salt, and ODN is a synthetic 25-base, single-stranded oligonucleotide that contains unmethylated CpG dinucleotides with a phosphorothioate backbone as a sodium salt. The structure of Pam2 and nucleotide sequence of ODN are shown in Figure 3.

Figure 3: Structure and Nucleotide Sequence of PUL-042 Components Pam2 and ODN Pam2

C = carbon; H = hydrogen; O = oxygen; S = sulfur; Ser = serine, Lys = lysine; MW = molecular weight

ODN

5'-TCG TCG TCG TTC GAA CGA CGT TGA T-3' M.W.: 8,049.5 (single-stranded, nuclease-resistant phosphorothioate oligodeoxynucleotides)

5.3. Nonclinical Studies

The nonclinical pharmacology, pharmacokinetics, and toxicology of PUL-042 are described in detail in the Investigator's Brochure.

5.4. Clinical Studies

The initial phase 1 study of PUL-042 Inhalation Solution (PUL-042-001) "A Randomized, Double-Blind, Placebo-Controlled, Ascending Dose Study to Assess the Safety, Tolerability, Pharmacokinetics and Pharmacodynamics of PUL-042 Inhalation Solution in Healthy Subjects" has been completed. Subjects were administered a single dose of PUL-042 Inhalation Solution by nebulization. A total of 4 mL of a solution of PUL-042 at increasing concentrations was administered using sterile water for injection (SWFI) as the diluent.

Review of the data from the PUL-042-001 study indicated that there was a potential pharmacodynamic effect indicated by a rise in the absolute neutrophil count (ANC) as measured at 4 hours post dose in subjects treated with PUL-042 Inhalation Solution compared to placebo. The ANC was at or near baseline levels when measured again at 24 hours post dose. All values were within the normal range at the 24-hour time point. The neutrophil response was confirmed in sheep and mice, and furthermore was shown to be dose dependent in mice. The time course of that response has been further explored in subjects in the study PUL-042-003 "A Randomized, Open-label, Crossover Study to Assess the Safety, Tolerability and Pharmacodynamics of PUL-042 Inhalation Solution in Healthy Subjects and the Effect of Pretreatment with Cromolyn Sodium or Albuterol Sulfate".

A similar potential pharmacodynamic effect was seen in the spirometry data (specifically the forced expiratory volume in 1 second [FEV1]) from PUL-042-001, likely due to the effect of PUL-042 on the bronchial airways. A dose-dependent decrease in FEV1 was seen with a nadir at approximately 30 minutes post-dose in subjects treated with PUL-042 Inhalation Solution. There was no comparable decline observed with placebo. These measurements were largely within the 12% change from baseline accepted as normal variability. This was followed by a recovery to near baseline levels at 24 hours post dose. Over the course of 7 days, the mean FEV1 was within 0-5% of the baseline value, with the subjects who received higher doses of PUL-042 showing a larger mean decrease in FEV1. None of the decreases in FEV1 were accompanied by signs of respiratory distress or a drop in oxygen saturation. None of the FEV1 results in the PUL-042 inhalation treated groups were statistically different from placebo after the 30-minute time point. The MTD delivered as a single dose was established as 40.6 µg Pam2 : 59.5 µg ODN in PUL-042-001.

A second phase 1 study (PUL-042-003) has been completed. PUL-042-003 was a randomized, open-label, cross-over study to determine the safety and tolerability of PUL-042 Inhalation Solution and to explore the effect of pretreatment with either cromolyn sodium or albuterol sulfate. The primary objective of this study was to determine the safety and tolerability in healthy normal subjects of single or repeated doses of PUL-042 in SWFI. Exploratory objectives include determining whether ANC was an indicator of biological activity and to determine 1) the duration of local biological activity in the bronchial airways by serial FEV1 measurements, 2) whether the administration of cromolyn sodium prior to the administration of PUL-042 had an effect on the FEV1 response, and 3) whether the administration of albuterol prior to the administration of PUL-042 had an effect on the FEV1 response.

In protocol PUL-042-003, the first cohort of 8 subjects (cohort 1) received a dose of 20.3 μ g Pam2 : 29.8 μ g ODN (1/2 the single-dose MTD of PUL-042) with or without pretreatment with cromolyn sodium (4 each). Subjects were then crossed over to the alternative treatment after a 2-week follow-up period and an additional 2-week washout period.

A similar design was used for the second cohort (8 subjects) with PUL-042 +/- albuterol sulfate. The second cohort of subjects received a total dose of 40.6 μ g Pam2 : 59.5 μ g ODN as two doses over 3 days (1 dose on Day 1 and 1 dose on Day 3) and a total dose of 81.2 μ g Pam2 : 119 μ g ODN as four doses over 32 days (1 dose each on Day 1, Day 3, Day 29 and Day 32).

Results from PUL-042-003 showed no clinically significant abnormalities or changes from baseline for vital signs, electrocardiography, pulse oximetry, physical examination, or safety laboratory assessments.

In general, FEV1 results were consistent with those seen in PUL-042-001 with an early onset decrease in FEV1 in some subjects that spontaneously reversed to near baseline levels over several minutes to hours. In the PUL-042-001 study, a small decrease in average FEV1 was also observed 7 days post-treatment (the last observation in that study) compared to the pre-dose baseline. A similar pattern was observed through 7 days post-treatment in PUL-042-003. Observations at later time points showed sporadic decreases in FEV1 values, but longer-term follow-up measurements of FEV1 gave results comparable to the initial pre-dose baseline values. As in study PUL-042-001, none of the decreases in FEV1 were accompanied by signs of respiratory distress or a drop in oxygen saturation. Pre-treatment with cromolyn sodium or albuterol sulfate had no significant effect on the short lasting FEV1 decreases observed following administration of PUL-042.

Currently there is an ongoing Phase 2 study, PUL-042-402 (A Phase 2, Single-Center, Double-Blind, Placebo-Controlled Study of PUL-042 Inhalation Solution in Rhinovirus-induced Symptoms in Current Smokers with GOLD Stage 0 COPD), that is evaluating the effects of PUL-042 on peak lower respiratory symptoms and safety in subjects with an experimentally induced rhinovirus infection with laboratory human rhinovirus strain HRV A16.

Subjects are dosed with PUL-042 (20.3 µg Pam2 : 29.8 µg ODN [50 µg PUL-042]) or placebo 24 hours prior to viral inoculation and again 48 hours post inoculation. The subjects are then followed for 6 weeks. To date, 19 of the planned 24 subjects have completed the study and data from 18 subjects reviewed by the Data Safety Monitoring Board (DSMB). The DSMB approved enrolling 6 additional subjects based on the data from these subjects. The study has been suspended due to the COVID-19 pandemic but, is anticipated to re-start in Q4 2020. The study remains blinded to treatment related efficacy and safety. There have been no Serious Adverse Events reported and no apparent safety concerns with PUL-042 administration following a respiratory viral infection.

5.5. Dosing

The dose selected is based on the results of PUL-042-001, a single ascending dose study to determine the maximum tolerated dose of PUL-042 in healthy volunteers, PUL-042-003, an open-label crossover study to investigate the effects of pretreatment with cromolyn sodium or albuterol sulfate on the safety, tolerability, and pharmacodynamics of PUL-042 administered to healthy volunteers, and PUL-042-402 an ongoing double-blind study of PUL-042 in a COPD rhinovirus challenge model.

Based on the results of these studies, the dose level of PUL-042 Inhalation Solution in the current study will be 20.3 μ g Pam2 : 29.8 μ g ODN/mL (50 μ g PUL-042 [this is the same dose level currently used in the ongoing viral challenge study]). A total of up to 4 doses will be administered over a 10 day period for a total dose of 81.2 μ g Pam2 : 119.2 μ g ODN.

Doses of PUL-042 or placebo will be prepared by an unblinded pharmacist and administered to the subject within 4 hours of preparation. Further details will be supplied in a pharmacy manual.

Doses will be administered via nebulization to deliver 4 mL using a PARI Sprint nebulizer equipped with a filter valve to prevent aerosol generation. The nebulizer will be operated until all drug is delivered. Each nebulizer will be dedicated to each subject during participation in the study. A new filter pad will be used in the filter valve for each administration of PUL-042. A nose clip will be used during the nebulization procedure.

Despite the use of the above nebulization equipment health care professionals should wear appropriate personal protective equipment and observe the procedure from a distance of at least six feet or preferably from another room until after nebulization has been completed.

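### The dose level is written per mL, but 20.3 : 29.8 mcg is the amount per 4 mL dose; as written, four doses give four times the stated total

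*Protocol*

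**What the plan says.** Protocol 5.5 sets the dose level at 20.3 mcg Pam2 : 29.8 mcg ODN per mL, labels it 50 mcg PUL-042, and adds that "this is the same dose level currently used in the ongoing viral challenge study". On volume it says "Doses will be administered via nebulization to deliver 4 mL using a PARI Sprint nebulizer"; Protocol 7.10.2 and 7.11.2 confirm that the volume is a constant 4 mL and that the nebulizer runs until all of it is delivered. On the total, 5.5 says "A total of up to 4 doses will be administered over a 10 day period for a total dose of 81.2" mcg Pam2, paired with 119.2 mcg ODN. SAP 3.2.3 repeats the per-mL level, the 50 mcg label, the 4 mL volume and the total.

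Protocol 5.4 describes the earlier studies from which the dose was chosen:

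- PUL-042-001: "A total of 4 mL of a solution of PUL-042 at increasing concentrations was administered". "The MTD delivered as a single dose was established as 40.6" mcg Pam2 : 59.5 mcg ODN.
- PUL-042-003, first cohort: a dose of 20.3 mcg Pam2 : 29.8 mcg "ODN (1/2 the single-dose MTD of PUL-042) with or without pretreatment with cromolyn sodium".
- PUL-042-003, second cohort: 40.6 : 59.5 mcg in total as two doses, and 81.2 mcg Pam2 : 119 mcg "ODN as four doses over 32 days (1 dose each on Day 1, Day 3, Day 29 and Day 32").
- PUL-042-402, the viral challenge study: "Subjects are dosed with PUL-042 (20.3" mcg Pam2 : 29.8 mcg ODN, labelled 50 mcg PUL-042), with no per-mL unit.

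**The concern.** A concentration, a volume per dose, a number of doses and a cumulative total are all given, so any one of them can be checked against the other three. They do not agree. One coincidence makes this easy to miss: 20.3 mcg/mL times 4 mL is 81.2 mcg, so on the per-mL reading the figure printed as the four-dose total is the content of a single dose.

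The dose is a basic specification of the trial, and here it contradicts itself in both documents. Protocol 9.5 has the site pharmacist dilute the components to the appropriate concentration without giving a number, so 5.5 holds the only numeric concentration in the protocol. Protocol 7.5 allows up to 20 centers. A four-fold over-concentration would not change the 4 mL volume, so blinded staff would have little to alert them. Protocol 5.4 reports FEV1 decreases that grow with dose.

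**Working it through.** **Inputs.** Level 20.3 : 29.8 mcg, written per mL (Protocol 5.5, SAP 3.2.3); volume 4 mL per dose (Protocol 5.5, 7.10.2); up to 4 doses (Protocol 5.5); stated total 81.2 : 119.2 mcg (Protocol 5.5, SAP 3.2.3); single-dose MTD 40.6 : 59.5 mcg, given in 4 mL (Protocol 5.4).

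**Step 1. Reproduce the stated total.** If 20.3 : 29.8 mcg is the amount in one dose, total = amount per dose × number of doses:

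- Pam2: 20.3 × 4 = 81.2 mcg
- ODN: 29.8 × 4 = 119.2 mcg

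Both match exactly.

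**Step 2. Apply the unit as written.** Amount per dose = concentration × volume; total = amount per dose × 4:

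- Pam2: 20.3 × 4 = 81.2 mcg per dose; 81.2 × 4 = 324.8 mcg in total
- ODN: 29.8 × 4 = 119.2 mcg per dose; 119.2 × 4 = 476.8 mcg in total
- Ratio to the stated total: 324.8 / 81.2 = 4.0 and 476.8 / 119.2 = 4.0

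**Step 3. Decide which element is wrong.**

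| Check | Arithmetic | Per-dose reading | Per-mL reading |
|---|---|---|---|
| Half the MTD (PUL-042-003, first cohort) | 40.6 / 2 = 20.3; 59.5 / 2 = 29.75 | agrees | one dose is 81.2 / 40.6 = 2.0 and 119.2 / 59.5 = 2.003 times the MTD |
| Two-dose total in PUL-042-003 | 40.6 / 2 = 20.3; 59.5 / 2 = 29.75 | agrees | one dose would be 81.2 : 119.2 |
| Four-dose total in PUL-042-003 | 81.2 / 4 = 20.3; 119 / 4 = 29.75 | agrees | one dose would be 81.2 : 119.2 |
| The 50 mcg label | 20.3 + 29.8 = 50.1 | agrees | 4 × 50.1 = 200.4 mcg per dose |
| Same level as PUL-042-402 | 20.3 : 29.8 mcg given as the dose | agrees | four times that dose |

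The differences between 29.75 and 29.8, and between 119 and 119.2, are rounding.

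**Step 4. Concentrations in 4 mL.**

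- MTD: 40.6 / 4 = 10.15 and 59.5 / 4 = 14.875 mcg/mL. The written 20.3 : 29.8 mcg/mL is about twice this.
- Intended dose: 20.3 / 4 = 5.075 and 29.8 / 4 = 7.45 mcg/mL.

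**The case against.** The inconsistency is not in dispute; the case on the other side is that it is minor. The paragraph that contains the stray unit also gives the 50 mcg label, the link to the challenge study and the four-dose total, so a careful reader recovers the intended dose. Taken as a whole, the text contradicts itself rather than prescribing twice the MTD. Preparation instructions are left to the Pharmacy Manual (Protocol 5.5, 9.2, 9.5), so pharmacists are not told to dilute from 5.5. The SAP passage is descriptive, and SAP 7.1 summarises the number of doses, minutes of administration and whether the full 4 mL was delivered, not micrograms.

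All of this stands as a limit on the consequence. An actual misdosing is not shown, and no estimate, test or exposure table changes. It does not make the point a background typo. The error sits in the trial's own dose statement, appears in both documents, and supplies the protocol's only numeric concentration for a drug diluted at the sites. It is also true that the stated total is correct and that deleting the unit would remove the contradiction. Giving the concentration as well goes further, but it follows directly from the fixed 4 mL volume and gives the sponsor a figure to check against the Pharmacy Manual.

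**Conclusion.** The dose level is wrong as written in Protocol 5.5 and SAP 3.2.3. The error is a unit and its size is a factor of four: 324.8 : 476.8 mcg over four doses as written, against the stated 81.2 : 119.2 mcg; per administration, 81.2 : 119.2 mcg against an intended 20.3 : 29.8 mcg. The direction is not in doubt, because the half-MTD statement, the two totals in PUL-042-003, the challenge-study dose, the 50 mcg label and the stated total all agree with the per-dose reading and none agrees with the per-mL reading.

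This rests on the 4 mL volume per dose, which the protocol states repeatedly. The effect on planned analyses is nil. The practical risk of misdosing cannot be judged without the Pharmacy Manual. It should be corrected.

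**What to change.** In Protocol 5.5 and SAP 3.2.3, give the dose level as 20.3 mcg Pam2 : 29.8 mcg ODN per 4 mL dose (5.075 : 7.45 mcg/mL). Keep the 50 mcg label and the total of 81.2 : 119.2 mcg. Confirm that the dilution instructions in the Pharmacy Manual yield 5.075 : 7.45 mcg/mL in 4 mL.

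The cost is one unit corrected in two documents and one check of the manual. No subjects, procedures or analyses are added.

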6. STUDY OBJECTIVES

6.1. **Primary Objective**

To determine the efficacy of PUL-042 Inhalation Solution in the prevention of viral infection with SARS-CoV-2 and progression to COVID-19 in subjects: 1) who have repeated exposure to individuals with SARS-CoV-2 infection, and 2) are asymptomatic at enrollment.

The primary endpoint is the severity of COVID-19 as measured by the maximum difference from the baseline value in the Ordinal Scale for Clinical Improvement within 28 days from the start of experimental therapy.

6.2. Secondary Objective

To determine the difference in incidence of SARS-CoV-2 infection 28 days from the start of experimental therapy in subjects who test negative for SARS-CoV-2 at the pre-treatment visit

To determine the difference in incidence of SARS-CoV-2 infection 14 days from the start of experimental therapy in subjects who test negative for SARS-CoV-2 at the pre-treatment visit

To compare the severity of COVID-19 within 14 days from the start of experimental therapy

To compare the severity of COVID-19 within 28 days from the start of experimental therapy

To assess the requirement for ICU admission within 28 days from the start of experimental therapy

To assess the requirement for mechanical ventilation within 28 days from the start of experimental therapy

To assess mortality within 28 days from the start of experimental therapy

To determine the tolerability of PUL-042 Inhalation Solution in this population

7. INVESTIGATIONAL PLAN

7.1. Overall Study Design

This will be a double-blind trial. A total of 200 subjects randomized 1:1 (PUL-042 Inhalation Solution: placebo) will be enrolled in the trial.

Doses will be administered via nebulization with a PARI sprint nebulizer. All subjects will receive up to 4 doses of PUL-042 Inhalation Solution or placebo over 10 days (Days 1, 3, 6, and 10).

Note: There is no Day 0 in this study.

An overview of the study design is presented in Figure 4.

Figure 4 Study Design

PUL-042-501 STUDY OVERVIEW

7.2. Subject Selection

7.2.1. Inclusion Criteria

Subjects aged 18 years or older must fulfill all of the following inclusion criteria to be eligible for the study:

- 1. Subjects must have recent exposure to SARS-CoV-2 (such as repeated or extensive exposure to an infected individual(s) or cohabiting with a SARS-CoV-2 positive individual).
- 2. Subjects must be 50 years or older if the exposure is due to cohabitation.
- 3. Subjects must be free of clinical signs or symptoms of a potential COVID-19 diagnosis (Ordinal Scale for Clinical Improvement score of 0) with a SARS-CoV-2 infection symptom score (fever, cough, shortness of breath, and fatigue) of 0 in each category.
- 4. Spirometry (forced expiratory volume in one second FEV₁ and forced vital capacity [FVC]) ≥70% of predicted value.
- 5. If female, the subject must be surgically sterile or ≥ 1 year postmenopausal. If of child-bearing potential (including being < 1) years postmenopausal) and, if participating in sexual activity that may

lead to pregnancy, the subject agrees to use an effective dual method of birth control (acceptable methods include intrauterine device, spermicide, barrier, male partner surgical sterilization, and hormonal contraception) during the study and through 30 days after completion of the study.

- 6. If female, must not be pregnant, plan to become pregnant, or nurse a child during the study and through 30 days after completion of the study. A pregnancy test must be negative at the Screening Visit, prior to dosing on Day 1.
- 7. If male, must be surgically sterile or, if not surgically sterile and if participating in sexual activities that may lead to pregnancy, be willing to practice two effective methods of birth control (acceptable methods include barrier, spermicide, or female partner surgical sterilization) during the study and through 30 days after completion of the study.
- 8. Ability to understand and give informed consent.

